Furthermore, secukinumab 300 mg was more efficacious than 150 mg in achieving clinically meaningful improvements in skin disease, particularly with respect to clear/almost clear skin (PASI 90, IGA mod 2011 0/1) in patients with moderate to severe psoriasis (defined as  $\geq 10\%$  BSA). There was a clear dose response favoring secukinumab 300 mg in the higher thresholds of skin clearance. The difference between 300 mg and 150 mg secukinumab regimens was more pronounced in the more difficult-to-achieve PASI 90 and IGA mod 2011 0/1 endpoints, with 21.9% and 27.4% more patients with  $\geq 10\%$  BSA compared to 8.2% and 3.3% more patients with  $< 10\%$  BSA reaching PASI 90 and IGA mod 2011 0/1 responses, respectively, at Week 24. Therefore, secukinumab 300 mg afforded greater improvement in plaque psoriasis than 150 mg, particularly in the achievement of clear/almost clear skin, in patients with moderate to severe psoriasis ( $\geq 10\%$  body surface area).

Two case reports of patients suffering from GCA and PsA in remission (either glucocorticoid-free remission or low-dose glucocorticoid remission) after treatment with secukinumab strengthens the idea of IL-17A inhibition to be a new mode of action in the treatment of GCA (Rotar et al 2018, Sammut et al 2018).

In addition, pertaining to safety assessment, there were no clinically meaningful differences among the secukinumab doses of 300 mg and 150 mg in the exposure adjusted incidences rates of the key risks over the entire treatment period in the 2 Phase III trials in PsA patients.

The overall safety in the PsA population was consistent with prior extensive experience in psoriasis, and showed that secukinumab 300 mg and 150 mg are acceptable for chronic use in adult patients with active PsA.

For the primary analysis, a treatment duration of 24 weeks was selected for this study. This is shorter than the 52-week treatment duration in the GiACTA trial ([Stone et al 2017](#)); however, most flares occurred within the first 6 months in the GiACTA trial. Therefore, the time point for primary analysis is at Week 28, to evaluate the effect of secukinumab in patients are on study treatment or placebo for 24 weeks. Assessments for the primary analysis will be conducted at Week 28, 2 weeks after last prednisolone dose in Week 26.

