### **5.5.4 Instructions for prescribing and taking study treatment**

The study treatment schedule is presented in Table 5-2. Secukinumab (2 × 150 mg in 1.0 mL PFS) or matching placebo will be administered s.c. to the patient throughout the study. Patients will be given the injections on site by qualified staff at all scheduled study visits.

The injections will be administered into the appropriate site of the body (thighs, arms, abdomen) and each injection should be given at a different injection site to reduce the risk of reaction. Each new injection should be given at least one inch from the previously used site. If the abdomen is chosen, a 2-inch area around the navel should be avoided. The study treatment should not be injected into areas where the skin is tender, bruised, red or hard, or where the subject has scars or stretch marks.

Single PFS will be packaged in boxes. Prior to administration the boxes containing the PFS with study treatment solution should be allowed to come to room temperature unopened for 15 to 30 minutes prior to injection. Used PFS should be disposed immediately after use in a sharps container OR according to local regulations.

For visits scheduled through Week 4, the study treatment should not be administered less than 7 days from the previous administration. For visits scheduled after Week 4, the study treatment should not be administered less than 14 days from the previous administration.

Prednisolone will be co-administered to all patients in a tapered regimen from their Baseline dose (i.e. 25 mg to 60 mg) to 1 mg at Week 26 (last dose of prednisolone, 0 mg from Week 27 onwards).

Patients will be given prednisolone tablets by the site staff on site at study site visits, and will be supplied with sufficient tablets for home administration between study visits. The investigator must promote compliance by instructing the patient to take prednisolone exactly as prescribed and by stating that compliance is necessary for the patient's safety and the validity of the study. The patient must be able to contact the investigator at any time if he/she is unable for any reason to take prednisolone as prescribed.

Sponsor qualified medical personnel will be readily available to advise on trial related medical questions or problems.

All dosages prescribed and dispensed to the patient and all dose changes during the study must be recorded on the eCRF.

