### **5.5.5 Permitted dose adjustments and interruptions of study treatment**

Study treatment interruption should be avoided with the following exceptions:

- Study treatment interruption is only permitted if, in the opinion of the investigator, a patient is deemed to be placed at a significant safety risk unless dosing is temporarily interrupted. In such cases study treatment should be interrupted only during the time that this risk is present and ongoing. Study treatment can be restarted at the next scheduled visit after resolution of the safety risk.

Any study treatment interruption must be recorded on the corresponding CRF page.

No dose escalation is permitted in this study. Prednisolone dosing will be tapered down weekly from Baseline through to Week 26 as indicated in [Section 5.5.4](#).

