##### **Prednisolone from Baseline**

Patients will receive a daily dose of prednisolone, which will be decreased (i.e. tapered down) from Baseline to Week 26 as described in [Section 5.5.4](#). No additional prednisolone or equivalent is permitted.

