2.1.1 General definitions

2.1.1.1 Treatment

Study treatment

At Baseline, patients will be assigned to one of the following two arms in a 1:1 ratio:

- Group 1: secukinumab 300 mg subcutaneous (s.c.) + 26-week prednisolone taper regimen
- Group 2: placebo s.c. + 26-week prednisolone taper regimen

The study treatment is secukinumab 300 mg supplied in prefilled syringes (PFS) each containing 150 mg of secukinumab, or placebo supplied in PFS to match secukinumab dose.

Co-administered treatment

The co-administered treatment refers to prednisolone tablets for tapered oral administration (taper regimen from a dose of 25 mg to 60 mg at Baseline to 0 mg at Week 28). Prednisolone will be supplied as 1 mg, 5 mg, 10 mg, 20 mg tablets.

Note: Prednisolone may continue to be taken after the 26-week prednisolone taper regimen.

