22	Week 19	Study day 134 to Study day 140
23	Week 20	Study day 141 to Study day 147
24	Week 21	Study day 148 to Study day 154
25	Week 22	Study day 155 to Study day 161
26	Week 23	Study day 162 to Study day 168
27	Week 24	Study day 169 to Study day 175
28	Week 25	Study day 176 to Study day 182
29	Week 26	Study day 183 to Study day 189
30	Week 27	Study day 190 to Study day 196
31	Week 28	Study day 197 to Study day 203
32	Week 29	Study day 204 to Study day 210
33	Week 30	Study day 211 to Study day 217
34	Week 31	Study day 218 to Study day 224
35	Week 32	Study day 225 to Study day 231
36	Week 33	Study day 232 to Study day 238
37	Week 34	Study day 239 to Study day 245
38	Week 35	Study day 246 to Study day 252
39	Week 36	Study day 253 to Study day 259
40	Week 37	Study day 260 to Study day 266
41	Week 38	Study day 267 to Study day 273
42	Week 39	Study day 274 to Study day 280
43	Week 40	Study day 281 to Study day 287
44	Week 41	Study day 288 to Study day 294
45	Week 42	Study day 295 to Study day 301
46	Week 43	Study day 302 to Study day 308
47	Week 44	Study day 309 to Study day 315
48	Week 45	Study day 316 to Study day 322
49	Week 46	Study day 323 to Study day 329
50	Week 47	Study day 330 to Study day 336
51	Week 48	Study day 337 to Study day 343
52	Week 49	Study day 344 to Study day 350
53	Week 50	Study day 351 to Study day 357
54	Week 51	Study day 358 to Study day 364
55	Week 52	Study day 365 to Study day 371
56	Week 53	Study day 372 to Study day 379
57	Week 54	Study day 380 to Study day 386
58	Week 55	Study day 387 to Study day 393
59	Week 56	Study day 394 to Study day 400

Page 17 of 53

Timepoint	Week	Week definition
60	Week 57	Study day 401 to Study day 407
61	Week 58	Study day 408 to Study day 414
62	Week 59	Study day 415 to Study day 421
63	Week 60	Study day 422 to Study day 429

Note: Co-administered treatment refers to prednisolone taken for GCA. There should be a 26-week prednisolone taper regimen however a patient may take additional prednisolone over the 52-week treatment period.

2.2 **Analysis sets**

The following analysis sets will be used for the patients of interest:

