2.7.1 Secondary endpoints

The following secondary endpoints will be analyzed:

- Proportion of GCA patients who adhere to the prednisolone taper regimen and are in sustained remission at Week 52
- Remission rate at Week 12
- Time to first GCA flare after Baseline (up to and including Week 52)
- Total cumulative prednisolone dose from start of co-administered treatment to Week 28, 52
- Proportion of patients on prednisolone dose ≤ 5 mg/day at Week 19, 28, 52
- Change from Baseline in PhGA VAS at Week 4, 8, 12, 16, 20, 24, 28, 36, 44 and 52
- Change from Baseline in PGA VAS at Week 4, 8, 12, 16, 20, 24, 28, 36, 44 and 52
- Change from Baseline in FACIT-Fatigue at Week 4, 8, 12, 16, 20, 24, 28, 36, 44 and 52
- Change from Baseline in SF-36 at Week 4, 8, 12, 16, 20, 24, 28, 36, 44 and 52
- Change from Baseline in EQ-5D at Week 4, 8, 12, 16, 20, 24, 28, 36, 44 and 52
- Change from Baseline in CRP (mg/L) at Week 4, 8, 12, 16, 20, 24, 28, 36, 40, 44, 48, 52
- Change from Baseline in ESR (mm/hr) at Week 4, 8, 12, 16, 20, 24, 28, 36, 40, 44, 48, 52

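### The Week 28 primary assessment falls 8 days, not 2 weeks, after the last scheduled prednisolone dose; its window overlaps the taper, and SAP 2.7.1 omits Week 32 for CRP and ESR

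*Protocol*

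**What the plan says.** Protocol 3.3, explaining the choice of time point: "Assessments for the primary analysis will be conducted at Week 28, 2 weeks after last prednisolone dose in Week 26".

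On the taper itself:

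- Protocol 5.5.4 takes the dose "to 1 mg at Week 26 (last dose of prednisolone, 0 mg from Week 27 onwards". Tables 5-3 and 5-4 agree: 1 mg/day in the Week 26 row, 0 in the rows for Weeks 27 and 28. The protocol summary also puts 0 mg at Week 27.
- Protocol 5.5 gives the planned prednisolone duration as 26 weeks.
- SAP 2.1.1.1 describes a "taper regimen from a dose of 25 mg to 60 mg at Baseline to 0 mg at Week 28".

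On timing, SAP 2.1.1.12 defines prednisolone Week 26 as "Study day 183 to Study day 189" and Week 27 as "Study day 190 to Study day 196" (Table 2-2). It gives the Week 28 visit a target of Day 197 and a window of Days 184 to 211 (Table 2-1).

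On the inflammatory markers, SAP 2.7.1 lists "Change from Baseline in CRP (mg/L) at Week 4, 8, 12, 16, 20, 24, 28, 36, 40, 44, 48, 52". The ESR list has the same weeks. SAP Table 1-1 and protocol 9.5.1 both include Week 32.

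**The concern.** A reader of protocol 3.3 would understand that each patient seen on schedule has been off prednisolone for two weeks when the primary endpoint is assessed. If the tables give about half of that, the rationale misdescribes what a Week 28 responder has shown. The results are meant to inform a Phase III programme.

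The visit window adds to this. An assessment made during the last taper week can be labelled Week 28, and nothing in the SAP flags it. A taper end and length that vary between passages leave the programmer to choose, and taper length enters the adherence rule that is part of the primary endpoint. The missing Week 32 removes from the operative list the first CRP and ESR visit scheduled after Week 28.

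**Working it through.** **Inputs**

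- Dosing frequency, protocol 5.5.7.1: "Patients will receive a daily dose of prednisolone, which will be decreased (i.e. tapered down) from Baseline to Week 26".
- Step length, protocol 5.5.5: "Prednisolone dosing will be tapered down weekly from Baseline through to Week 26".
- Last non-zero step: Week 26 (protocol 5.5.4, Tables 5-3 and 5-4).
- Day ranges of weeks: SAP Table 2-2. Up to Week 28 they follow one formula: Week w covers Days 7w + 1 to 7w + 7.
- Visit targets, SAP Table 2-1: Week 24 = Day 169, Week 28 = Day 197, Week 32 = Day 225.

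**1. The plan's own figure.** Two weeks comes from subtracting week labels: 28 - 26 = 2, or in days 197 - 183 = 14. This treats the first day of Week 26 as the last dosing day.

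**2. The figure from the tables.** Week 26 runs from 7 × 26 + 1 = 183 to 7 × 26 + 7 = 189. With daily dosing the last scheduled dose is on Day 189.

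| Reading of the last dosing day | Day | Days to Day 197 |
|---|---|---|
| First day of Week 26 (labels only) | 183 | 14 |
| Strict 26 weeks, 26 × 7 | 182 | 15 |
| Last day of Week 26 | 189 | 8 |
| Dosing through Week 27, 0 mg first at Week 28 | 196 | 1 |

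Only the third row fits both daily dosing in Week 26 and 0 mg from Week 27. It leaves Days 190 to 196, which is 7 days, free of prednisolone before the target visit.

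**3. The Week 28 window.** Days 184 to 211 are 211 - 184 + 1 = 28 days:

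- 184 to 189: 6 days, prednisolone still scheduled.
- 190 to 202: 13 days, less than 14 days after Day 189.
- 203 to 211: 9 days, at least 14 days after Day 189.

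A visit on Days 184 to 189 would be 13 to 8 days before target. The minimum injection gap does not rule it out: after Week 4 that gap is 14 days, and 184 - 169 = 15.

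**4. Taper length.** Weeks 0 to 26 are 27 dosed rows, or 27 × 7 = 189 days, against 26 × 7 = 182 for the stated 26 weeks. SAP 2.5.1 counts a patient as non-adherent if prednisolone is taken for under 80% of the 26-week period. 0.80 × 182 = 145.6 and 0.80 × 189 = 151.2, so a patient with 146 to 151 days passes this criterion on one length and fails on the other.

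**5. CRP and ESR.** Protocol 9.5.1 and SAP Table 1-1 list 13 visits. SAP 2.7.1 lists 12, and the missing one is Week 32. Protocol Table 6-1 collects both markers at Week 32. SAP Section 4, which sets out changes from the protocol, does not mention it. Week 32 is 225 - 189 = 36 days after the last scheduled dose.

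**The case against.** The case for leaving the plan alone has several sound parts.

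- Protocol 3.3 is rationale, and the protocol does not number the days within a week. No prior, posterior, sample size or GO criterion uses the interval. This stands, and it limits the consequence. It does not make the sentence correct.
- The primary endpoint is no flare until Week 28 plus adherence to the taper. It requires no prednisolone-free time; that belongs to the Week 52 definition in the protocol. Disease activity is also assessed at every visit, so Week 28 is not the only look. A reader might infer that responders have failed to show what the endpoint claims. The definition does not support that.
- A reader might take SAP 2.1.1.1 to mean that dosing continues through Week 27. The sentence does not say 0 mg is reached only at Week 28. It may describe the last row of the taper tables, which show 0 at both weeks, and SAP 2.5.1 ends its excess-dose check at Week 26. It is a wording difference to reconcile, not evidence of another schedule.
- The 6 + 13 + 9 split counts calendar days, not patients. The protocol asks for visits as close to the designated day as possible, and both blinded arms share the same windows. No directional bias is shown. The SAP's closest-to-target rule helps only where the window holds more than one record.
- Flares after Week 28 already enter the time-to-flare and Week 52 analyses.

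The Week 32 omission is a clerical matter in a descriptive list. It is separate from the interval, but still wrong as written.

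**Conclusion.** The two-week statement does not agree with the trial's tables: on schedule the interval is 8 days, with 7 prednisolone-free days. This assumes that SAP Table 2-2 numbers the taper weeks of Tables 5-3 and 5-4 and that dosing is daily through Week 26. The Week 28 window admits six scheduled prednisolone days out of 28. The taper-end and taper-length passages differ, and Week 32 has dropped out of the CRP and ESR lists with no declared change.

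The effect on the primary result is likely small. The number of patients who would be seen on Days 184 to 189 cannot be derived from the documents and may be zero. It may be tempting to score early attenders at Week 32 in the primary analysis. That would mix Week 28 and Week 32 outcomes in a Week 28 estimand and give some patients longer at risk, so it is not recommended.

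**What to change.** 1. Reconcile the passages on when the taper reaches 0 mg (protocol summary, protocol 5.5.4, SAP 2.1.1.1) and on its length (protocol 5.5, Tables 5-3 and 5-4). State in SAP 2.5.1 the number of days on which the 80% criterion is based. Which schedule applies is for the sponsor to confirm.
2. In protocol 3.3, replace the two-week statement with the interval that follows from the reconciled schedule: 8 days on the present tables.
3. Restore Week 32 for CRP and ESR in SAP 2.7.1.
4. Keep the Week 28 estimand and window. Report, by arm, how many Week 28 assessments were made on or before the patient's last recorded taper dose.
5. Optionally, add a supportive summary of patients with no flare and no escape through Week 32. It partly overlaps the time-to-flare analysis.

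The cost is wording in two documents and one short table from data already collected. The stated prednisolone-free interval will look less favourable than it does now.

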### **3.4 Rationale for choice of comparator**

A placebo arm is included in this study because it is not known whether secukinumab can improve GCA. However, standard of care with corticosteroids (i.e. prednisolone as described in [Section 3.2.1](#)) will be given to both treatment groups throughout the study. Due to the nature of the disease and the outcome measures used, a placebo arm is necessary to obtain reliable efficacy measurements, to judge the size of the active treatment compared to change over time in the placebo group, and to reasonably attribute AEs to secukinumab.

### **3.5 Purpose and timing of interim analyses/design adaptations**

Three interim analyses will be conducted after

- 50% of patients complete Week 28
- 50% of patients complete Week 52
- 100% of patients complete Week 28

to receive preliminary results whether secukinumab is effective in GCA and to support Phase III program activities.

The final analysis will be conducted after all subjects complete the study at Week 60. All available data from all patients will be analyzed and summarized in one final CSR.

### **3.6 Risks and benefits**

As of 25-Jun-2017, over 28000 subjects have been enrolled in clinical studies with secukinumab with over 25000 healthy volunteers and patients having received active drug. In an analysis of completed, unblinded/open label trials and trials analyzed up to the primary efficacy endpoint, (not including blinded trials or trials with healthy volunteers) a total of 9632 patients were treated with secukinumab. Of these, 6319 patients were exposed for at least 1 year. Overall, 16134.63 patient-years of exposure to secukinumab are reported in this analysis. Overall, patients have received secukinumab across various indications (rheumatoid arthritis, AS, PsA, psoriasis, multiple sclerosis, uveitis, Crohn's disease, dry eye, polymyalgia rheumatica) at doses ranging from single and multiple doses of 0.1 mg/kg to 30 mg/kg i.v. and 25 mg to 300 mg s.c. Full safety results from all PsA, AS and psoriasis completed studies show that secukinumab generally is safe and well tolerated.

The safety profile observed in the latest DSUR (Issue 007: 26-Jun-2016 to 25-Jun-2017) is in line with the current known safety profile of secukinumab in moderate to severe psoriasis, PsA and AS.

For all 3 indications, secukinumab has shown an imbalance vs. placebo in total AEs, which was driven by infections, mainly non-serious upper respiratory tract infections during the placebo-controlled epoch of the trials (12 to 16 weeks depending on the protocol). This imbalance was not translated into infection SAEs and there was also no difference between 300 mg and 150 mg secukinumab in the overall rate of infections or in upper respiratory tract infections. In all indications, Candida infections were more frequent with secukinumab when compared to placebo and, in psoriasis trials, Candida infections were more common with the 300 mg dose compared to the 150 mg secukinumab regimen. The imbalance between the doses was limited to non-serious, localized mucosal or cutaneous candidiasis, with no reports of chronic or systemic disease in any treatment group. Across indications, Candida infections were responsive to standard treatment and did not necessitate discontinuation. No serious opportunistic infections were reported. No tuberculosis reactivation or viral hepatitis reactivation were observed in clinical trials, regardless of indication (psoriasis, PsA or AS).

Neutropenia was more frequently observed with secukinumab than with placebo, but most cases were mild, transient and reversible spontaneously.

The incidence of hypersensitivity AEs was slightly higher with secukinumab compared with placebo, with the difference mostly due to mild to moderate urticaria and eczema non-associated with systemic symptoms.

The incidence of selected rare events of interest (major adverse cardiovascular events (MACE) and malignancies) adjusted for exposure over 52 weeks was comparable to placebo in clinical trials across multiple indications.

There was no clear association between treatment with secukinumab and new onset of inflammatory bowel disease, but due to the potential involvement of the IL-17A pathway in the pathogenesis of the disease, it is not possible to rule out a potential increased risk of exacerbation.

Secukinumab 300 mg was comparable to 150 mg and both doses showed comparable safety to placebo and etanercept over 52 weeks of treatment.

Infections, neutropenia and hypersensitivity are important identified risks, while malignancies, major adverse cardiovascular events, immunogenicity, Crohn's disease, and hepatitis B reactivation are important potential risks. Interaction with live vaccines is an important potential interaction (and also included as an important potential risk).

No new safety signal was identified and no actions were taken for safety reasons during the reporting period of the latest DSUR.

It is anticipated that secukinumab will have beneficial effects for patients with GCA by inhibiting IL-17A-driven inflammation and thereby enabling patients to achieve and maintain remission. The placebo patients in the study will not have this benefit, however, they will be followed closely in order to identify any progress or need for additional therapy.

The risk to patients in this trial will be minimized by compliance with the eligibility criteria, close clinical monitoring and extensive guidance to the investigators, provided in the current version of the Investigator's Brochure (IB).

Taking into account the individual risks, the expected risk profile of secukinumab from a mechanism of action perspective in GCA is anticipated to be similar to that of the approved indications.

From the standpoint of the overall risk benefit assessment, the current trial with secukinumab is justified.

Women of child bearing potential must be informed that taking the study treatment may involve unknown risks to the fetus if pregnancy were to occur during the study, and agree that in order to participate in the study they must adhere to the contraception requirements outlined in [Section 4.2](#) (Exclusion criteria). If there is any question that the patient will not reliably comply, they should not be entered or continue in the study.

